9.2. Evaluation of Immunogenicity Data

Based on the respective evaluable populations, the following measures of immunogenicity will be reported for (a) ADA prevalence, (b) ADA incidence, (c) Transient/Persistent ADA, and (d) NAb incidence.

The numbers and percentages of participants within each ADA/NAb category described above will be summarized over the entire study period. In addition, the number and percentage of positive ADA and NAb samples will be summarized by nominal visit. ADA titer values in positive ADA samples will be summarized by visit, including median, Q1, Q3, minimum and maximum titer values. Summary statistics for time to ADA onset in ADA+ participants (i.e. participants with Treatment-Emergent ADA) will include median, Q1, Q3, minimum and maximum onset times. Summaries will be provided for each treatment arm and all active treatment groups for the compound of interest combined.

By participant listing of ADA/NAb result, titer, and corresponding PK concentration by participant ID number and visit, as well as participant-level ADA/NAb status, ADA type (persistent or transient), and time to ADA onset will be provided for all participants in the Immunogenicity Analysis Set. A separate listing will be produced for participants with any

positive ADA results. The ADA titer values in ADA+ participants will be plotted over time by individual participant grouped by treatment. For the purpose of plotting, samples with negative ADA result or undetectable titer will have the titer value imputed to zero and connected with the adjacent time points.

In order to evaluate the impact of ADA on PK, combined individual PK concentration-time profile plots by treatment group will be produced with ADA+ participants highlighted in red

The following ADA summary tables will be generated for (1) anti-GS-5423, (2) anti-GS-2872, and (3) both anti-GS-5423 and anti-GS-2872:

- Immunogenicity results over the entire study period, including calculation of ADA prevalence, incidence, and numbers and percentages as well as NAb incidence of participants in each ADA category.
- Numbers and percentages of positive ADA and NAb results by visit
- Median, Q1, Q3, minimum, maximum of titer values in positive ADA samples by visit
- Time to treatment-emergent ADA onset (median, Q1, Q3, minimum, maximum) in ADA+ participants

The following figures will be provided for each analyte, anti-GS-5423 and anti-GS-2872:

- Individual concentration vs. time profiles grouped by treatment, with ADA+ participants highlighted in red
- Individual ADA titer values over time grouped by treatment (ADA+ participants only)
 - ADA titer values less than the minimum reportable titer value and titer values for ADA-negative samples will be imputed to 0.

The following listings will be provided:

- Listing of ADA results, titer, NAb results and corresponding PK concentrations by participant ID and visit, as well as participant-level ADA status, ADA type (persistent or transient), time to ADA onset, and NAb status for all participants in the immunogenicity analysis set
- Same listing above in participants with any positive ADA result.

In addition, summary of immunogenicity results over the entire study period for ADA/NAb against both GS-5423 and GS-2872 will be included.

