1.1. Study Objectives and Endpoints

Primary Objective	Primary Endpoint

 To evaluate the efficacy of switching to a regimen of lenacapavir (LEN, Sunlenca®), GS-5423, and GS-2872 versus continuing on baseline oral antiretroviral (ARV) therapy (ART) as determined by the proportion of participants with HIV-1 RNA ≥ 50 copies/mL at Week 26 	
 Proportion of participants with HIV-1 RNA ≥ 50 copies/mL at Week 26 as determined by the United States (US) Food and Drug Administration (FDA)-defined snapshot algorithm
Secondary Objectives	Secondary Endpoints

 To evaluate the efficacy of switching to a regimen of LEN, GS-5423, and GS-2872 versus continuing on baseline oral ART as determined by the proportion of participants with HIV-1 RNA ≥ 50 copies/mL at Week 52 To evaluate the efficacy of switching to a regimen of LEN, GS-5423, and GS-2872 versus continuing on baseline oral ART as determined by the proportion of participants maintaining virologic suppression (HIV-1 RNA < 50 copies/mL) at Weeks 26 and 52 	
 Proportion of participants with HIV-1 RNA ≥ 50 copies/mL at Week 52 as determined by the US FDA-defined snapshot algorithm Proportion of participants with HIV-1 RNA < 50 copies/mL at Weeks 26 and 52 as determined by the US FDA-defined snapshot algorithm Changes from baseline in CD4+ T-cell counts at Weeks 26 and 52 Proportion of participants experiencing treatment-emergent adverse events (TEAEs)
Secondary Objectives	Secondary Endpoints

 To evaluate CD4+ T-cell counts at Weeks 26 and 52 To evaluate the safety and tolerability of the 2 treatment groups To evaluate the pharmacokinetics (PK) of GS-5423, GS-2872, and LEN To evaluate the immunogenicity of GS-5423 and GS-2872 	
 Trough concentrations at Weeks 26 and 52 and PK parameters (AUC_{0-t}, AUC_{last}, $t_{1/2}$, C_{max}, and T_{max}) for GS-5423, GS-2872, and LEN as appropriate Incidence of anti-GS-5423 and anti-GS-2872 antibodies

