3. GENERAL CONSIDERATIONS FOR DATA ANALYSES

The Week 52 interim analysis will include all data collected from the randomized and the extension phases of the study. Only data collected in the randomized phase (ie, randomized phase data) will be summarized by treatment group (except that the “by-visit” summary will be up to Week 52 only), if not specified otherwise. Data collected from both phases will be included in data listings. Data included in each phase are defined as follows:

Randomized Phase Data

- For participants who do not enter the extension phase (ie, not treated in the extension phase), all available data are considered as the randomized phase data.
- For participants who enter the extension phase (ie, treated in the extension phase), randomized phase data are defined as data collected **up to** and including the first dose date of the extension phase with the exception as follows: for AEs, concomitant medications, pregnancy, and death, only data collected **prior to** the first dose date of the extension phase are included. For PK/ADA, data collected up to and including the predose timepoint on the first dose date of the extension phase is included.

Extension Phase Data

Extension phase data are only available from participants who enter the extension phase of the study. Extension phase data are defined as data collected **after** the extension phase first dose date with the exception as follows. For AEs, concomitant medications, pregnancy, and death, data collected **on or after** the extension phase first dose date are included. For PK/ADA data, data at postdose on Study Day 1 (EXT) if applicable or after Study Day 1 (EXT) is assigned to the Extension Phase.

In general, analysis results will be presented using descriptive statistics. For categorical variables, the number and percentage of participants in each category will be presented; for continuous variables, the number of participants (n), mean, standard deviation (SD) or standard error (SE), median, first quartile (Q1), third quartile (Q3), minimum, and maximum will be presented.

All statistical tests will be 2-sided and performed at the 5% significance level unless otherwise specified.

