3.1.6. Immunogenicity Analysis Sets

The Immunogenicity analysis sets include the follows:

- Anti-TAB Immunogenicity Analysis Set will include all randomized participants who have received at least 1 dose of study drug (GS-5423) and have had at least 1 nonmissing value for anti-GS-5423 evaluation.
- Anti-ZAB Immunogenicity Analysis Set will include all randomized participants who have received at least 1 dose of study drug (GS-2872) and have had at least 1 nonmissing value for anti-GS-ZAB evaluation.
- Anti-TAB and Anti-ZAB Immunogenicity Analysis Set will include all randomized participants who have received at least 1 dose of study drugs of GS-5423 and GS-2872 and have had at least 1 nonmissing value for both anti-TAB and anti-GS-ZAB evaluation.

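### SAP 9.2 counts participant-level ADA results over the whole study at the Week 52 cut, so the ADA-incidence endpoint has no fixed follow-up and no usable baseline for crossed-over controls

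*SAP*

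**What the plan says.** - **Endpoint.** SAP 1.1 lists "Incidence of anti-GS-5423 and anti-GS-2872 antibodies" as a secondary endpoint. Neither document attaches a week to it. Protocol 8.9 asks for a summary by treatment group.
- **Counting period.** SAP 9.2 says participant-level ADA and neutralizing antibody categories "will be summarized over the entire study period". Its table list repeats this: "Immunogenicity results over the entire study period, including calculation of ADA prevalence, incidence". A closing sentence uses the same period for antibodies against both products.
- **General rule.** SAP 3 brings both phases into the Week 52 analysis, then says: "Only data collected in the randomized phase (ie, randomized phase data) will be summarized by treatment group", qualified by "if not specified otherwise". It also gives ADA its own boundary for randomized-phase data: "For PK/ADA, data collected up to and including the predose timepoint on the first dose date of the extension phase is included".
- **Timing of the cut.** SAP 2.1.1 runs the analysis once every participant has reached Week 52 or left the study.
- **Columns.** SAP 9.2: "Summaries will be provided for each treatment arm and all active treatment groups for the compound of interest combined". SAP 3.2 defines only Group 1 (the long-acting regimen) and Group 3 (SBR).
- **Membership and baseline.** The sets in SAP 3.1.6 require one dose of the antibody and one ADA value, with no phase limit. SAP 3.8.1 fixes the Group 3 baseline at or before Study Day 1 of the randomized phase. In SAP Table 13-2 the first Group 3 ADA sample is at Week 52.

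**The concern.** SAP 9.1 counts a participant as an ADA case if treatment-emergent ADA ever appears, so the proportion can only rise as samples and doses accumulate. If the period is the whole study up to a calendar cut, early enrollees in Group 1 add samples taken after a third or later dose, while the last enrollee adds none after Week 52. The resulting percentage matches no defined length of follow-up or number of doses.

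Persistent ADA moves in the same way, because one limb of its definition in SAP 9.1 rests on the last sampling time point of the study.

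Controls raise a separate problem. Those who switch at Week 52 enter the sets, and the baseline rule makes their predose Week 52 sample a post-baseline one.

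At stake is whether the ADA figure describes 52 weeks on the regimen, and so can be set directly beside the Week 26 and Week 52 efficacy and PK results and used to plan Phase 3.

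**Working it through.** The documents give no ADA rate or precision figure, so there is nothing on this point to reproduce. The planned group sizes (50 and 25, SAP 1.3) agree with the stated AE-detection chances: 1 − 0.95^50 = 92.3% and 1 − 0.95^25 = 72.3%.

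**Sampling (SAP Tables 13-1 and 13-2).** Group 1 has five post-baseline ADA samples through Week 52 (Weeks 4, 12, 26, 38, 52), then extension samples at Weeks 64, 78, 90 and 104. For Group 3 the first routine sample after the Week 52 dose is at Week 64.

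**Assumptions, none from the documents.** True 52-week incidence of 10%; constant hazard; ADA found only at scheduled samples; uniform accrual over A weeks; no dropout; all 25 controls cross over; visit windows ignored.

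**Cumulative incidence.** P(t) = 1 − 0.9^(t/52) gives 10.0% at Week 52, 12.16% at 64, 14.62% at 78, 16.67% at 90 and 19.0% at 104.

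**Group 1 column.** At the cut, follow-up is uniform from 52 to 52 + A weeks.
- A = 26: last sample at Week 52 for 12/26 and at Week 64 for 14/26. (12/26)(10.0) + (14/26)(12.16) = **11.2%**.
- A = 52: last sample at Weeks 52, 64, 78 and 90 for 12/52, 14/52, 12/52 and 14/52. 2.31 + 3.27 + 3.37 + 4.49 = **13.4%**.

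| Accrual A (weeks) | Group 1 column | First enrollee | Last enrollee | Crossovers with no post-dose sample |
|---|---|---|---|---|
| 13 | 10.2% | 12.2% | 10% | 92% (about 23 of 25) |
| 26 | 11.2% | 14.6% | 10% | 46% (about 12) |
| 39 | 12.4% | 16.7% | 10% | 31% (about 8) |
| 52 | 13.4% | 19.0% | 10% | 23% (about 6) |

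Across the same accrual spans, a true 5% reads 5.1% to 6.8% and a true 20% reads 20.3% to 26.3%. Cut at the Week 52 predose sample, the column stays at the true value for any A.

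**Persistent ADA.** Take a Group 1 participant first positive at Week 52. Enrolled late, that is the last sample, so the ADA is persistent. Enrolled early, with a negative Week 64 sample and no later positive, the same ADA is transient.

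**Group 3 baseline.** SAP 9.1 sets no baseline of its own. The general rule in SAP 3.8.3 uses the first dose of study drug unless specified differently. SAP 3.8.1 does specify differently for Group 3, and protocol 1.2 counts baseline oral ART as study drug. The ADA baseline is therefore missing for controls and the Week 52 predose sample is post-baseline. Under SAP 9.1, a missing baseline with a later positive is treatment-induced, and any post-baseline result makes a participant evaluable for incidence. A pre-existing positive thus becomes treatment-induced, and a crossover with no post-dose sample joins the denominator. SAP 3.8.2 removes that predose result from by-visit tables only.

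**If crossovers were pooled.** Their own incidence would be (14/26)(2.40) = 1.3% for A = 26 and 3.8% for A = 52. The combined figure would be (50 × 11.16 + 25 × 1.29)/75 = 7.9%, or (50 × 13.44 + 25 × 3.83)/75 = 10.2%.

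**The case against.** Four arguments have weight.

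1. **No breach of SAP 3.** A reader might infer that SAP 9.2 violates the randomized-phase rule. The documents do not support that, because the rule yields wherever another section specifies otherwise. SAP 9.2 can be read as doing so, or as merely contrasting participant-level status with the by-visit tables that follow. On the second reading the SAP 3 boundary already applies. This stands, but the two readings give different endpoint values and the SAP does not choose between them.

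2. **Pooling is not established.** A reader might also infer that crossovers are merged with Group 1. Results are given for each arm, the combined column is additional, and SAP 3.2 keeps crossovers in the SBR group. The combined column may mean Group 1 alone, and its plural wording may predate the removal of Treatment Group 2. This stands. With one active group, however, such a column adds information only if crossovers enter, so it needs defining.

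3. **The endpoint has no stated week.** Counting all observed ADA contradicts no declared estimand, and a 52-week window is partly a matter of preference. That is fair, but a figure whose follow-up is set by enrolment date is still poorly defined.

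4. **The effect is modest and recoverable.** In 50 participants, moving from 10% to 11.2% or 13.4% is about 0.6 or 1.7 people. The exact 95% interval for 5/50 is roughly 3% to 22%, and no test or decision rule depends on it. By-visit tables, onset times and listings would let a reader rebuild a Week 52 figure for Group 1, so it would go too far to say that comparison with the Week 52 results is impossible. This lowers the stakes without settling what the main table reports.

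**Conclusion.** The point holds as an unreconciled counting rule that leaves a secondary endpoint ill-defined, and it should be corrected. Followed literally, SAP 9.2 makes Group 1 ADA incidence and persistent-ADA status depend on enrolment date. The illustrative inflation is from 10% to about 11.2% (26-week accrual) or 13.4% (52-week accrual). It rests on an assumed ADA rate, hazard and accrual pattern. Crediting ADA continuously up to the cut would give 12.3% and 14.6%, but that overstates the effect because extension ADA is drawn only at scheduled visits.

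The Group 3 baseline problem needs no such assumption, since it follows from the SAP's definitions and sampling schedule. Its size depends on how many controls cross over, how many are positive before their first antibody dose, and how many lack a later sample at the cut.

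**What to change.** In SAP 9.1 and 9.2:

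1. For the secondary endpoint, report ADA and neutralizing antibody incidence and persistent or transient status for Group 1 only. Use randomized-phase ADA data as SAP 3 already defines them, through the Week 52 predose sample.
2. Report extension ADA, including Group 3 after crossover, in a separate table by weeks since first antibody dose and number of doses. Set the crossover baseline as the last sample before the first antibody dose, and require at least one later sample for the incidence denominator. A phase cut alone does not cure the Group 3 problem, because the randomized-phase boundary includes the Week 52 predose sample.
3. State that the combined column means Group 1 only, or drop it.

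The cost is SAP wording and one extra table. The downside is that ADA first arising after Week 52 appears in the extension table and not in the endpoint. Protocol 1.4.1.2 already cites Week 52 virologic results. If the Week 52 tables have been produced, the same output can be added as a labelled supplementary table, and the definitions carried into the Week 104 analysis planned in protocol 8.2.1.1.

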11. SOFTWARE

SAS® Software Version 9.4. SAS Institute Inc., Cary, NC, USA.

nQuery Advisor(R) Version 7.0. Statistical Solutions, Cork, Ireland.

Phoenix WinNonlin® 7.0 Pharsigh Corporation, Princeton, NJ, USA.

12. SAP REVISION

Revision Date (DD MMM YYYY)	Section	Summary of Revision	Reason for Revision

13. APPENDICES

- Appendix 1. Study Procedures Table
- Appendix 2. Flowchart of US FDA-defined Snapshot Algorithm (for Long Acting Switch Trial)
- Appendix 3. Programming Specifications

Appendix 1. Study Procedures Table

Table 13-1. Study Procedures Table (Treatment Group 1)

Study Procedure	Screening		Randomized Phase											Extension Phase ^u			ESDD ^c	Post Study Drug Follow up ^c	
	Visit 1	Visit 2 ^a	Day 1	Day 2 ^b	Day 8 ^b	Day 15 ^b	Wk 4	Wk 12	Wk 24	Wk 26	Wk 38	Wk 50	Wk 52	Wk 64, 90, 116, 142	Wk 76, 102, 128, 154	Wk 78, 104, 130, 156		PSD Day 30, 90, 180	PSD Day 270, 365
Visit Window (Days)			Within 28 Days of Screening Visit 2		± 3 Days			± 6 Days						± 6 Days				± 6 Days	
Written informed consent	X																		
Medical history	X	X																	
Review concomitant medications	X	X	X	X	X	X	X	X	X	X	X	X	X	X	X	X	X	X	X
Review AEs	X	X	X	X	X	X	X	X	X	X	X	X	X	X	X	X	X	X	X
Complete physical examination		X	X														X		
Focused physical examination							X	X		X	X		X	X		X		X	
Height		X																	
Weight		X	X				X	X		X	X		X	X		X	X	X	
Vital signs ^d		X	X				X	X		X	X		X	X		X	X	X	
Proviral DNA phenotype	X																		
Proviral DNA genotype	X																		
Chemistry ^e		X	X				X	X		X	X		X	X		X	X	X	
Hematology ^e		X	X				X	X		X	X		X	X		X	X	X	
TSH		X	X										X				X		

Study Procedure	Screening		Randomized Phase											Extension Phase ^b			ESDD ^c	Post Study Drug Follow up ^c	
	Visit 1	Visit 2 ^a	Day 1	Day 2 ^b	Day 8 ^b	Day 15 ^b	Wk 4	Wk 12	Wk 24	Wk 26	Wk 38	Wk 50	Wk 52	Wk 64, 90, 116, 142	Wk 76, 102, 128, 154	Wk 78, 104, 130, 156		PSD Day 30, 90, 180	PSD Day 270, 365
Visit Window (Days)			Within 28 Days of Screening Visit 2		± 3 Days			± 6 Days					± 6 Days					± 6 Days	
CD4+ and CD8+ T-cell count		X	X					X		X	X		X	X		X	X	X ^f	
Serum pregnancy test		X																	
FSH ^g		X																	
Urinalysis		X	X				X	X		X	X		X	X		X	X	X	
Urine pregnancy test ^h			X				X	X		X	X		X	X		X	X	X	X
HBV & HCV serology		X																	
HIV-1 RNA		X	X				X	X	X	X	X	X	X	X	X	X	X	X	
HIV-1 genotype/phenotype ⁱ				X															
HIV reservoir assay (PBMC) ^j			X							X			X			X			
CCI																			
eGFR		X	X				X	X		X	X		X	X		X	X	X	
ECG ^j		X	X							X			X			X			
Plasma storage samples for virology testing			X				X	X	X	X	X	X	X	X	X	X	X		
Immunogenicity (ADA) serum sample ^l			X				X	X		X	X		X	X		X	X	X	X

Study Procedure	Screening		Randomized Phase											Extension Phase ^b			ESDD ^c	Post Study Drug Follow up ^c	
	Visit 1	Visit 2 ^a	Day 1	Day 2 ^b	Day 8 ^b	Day 15 ^b	Wk 4	Wk 12	Wk 24	Wk 26	Wk 38	Wk 50	Wk 52	Wk 64, 90, 116, 142	Wk 76, 102, 128, 154	Wk 78, 104, 130, 156		PSD Day 30, 90, 180	PSD Day 270, 365
Visit Window (Days)			Within 28 Days of Screening Visit 2		± 3 Days			± 6 Days						± 6 Days				± 6 Days	
Serum PK samples (GS-5423 & GS-2872) ^{m, n}			X				X	X	X	X	X	X	X	X		X	X	X	X
Plasma PK sample for LEN ^{m, o}			X				X	X	X	X	X	X	X	X		X	X	X	X
																			
Randomization			X																
HIV Treatment Preference Questionnaire			X							X			X			X			
HIVDQoL			X							X			X			X			
HIVTSQs ^q			X				X			X			X			X			
HIVTSQc ^q										X									
LEN oral administration ^r			X	X															
LEN SC administration			X							X			X			X			
GS-5423 IV infusion administration ^s			X							X			X			X			

Study Procedure	Screening		Randomized Phase											Extension Phase ^b			ESDD ^c	Post Study Drug Follow up ^e	
	Visit 1	Visit 2 ^a	Day 1	Day 2 ^b	Day 8 ^b	Day 15 ^b	Wk 4	Wk 12	Wk 24	Wk 26	Wk 38	Wk 50	Wk 52	Wk 64, 90, 116, 142	Wk 76, 102, 128, 154	Wk 78, 104, 130, 156		PSD Day 30, 90, 180	PSD Day 270, 365
Visit Window (Days)			Within 28 Days of Screening Visit 2		± 3 Days			± 6 Days						± 6 Days				± 6 Days	
GS-2872 IV infusion administration ^s			X							X			X			X			

CCI

ADA = antidrug antibody; AE = adverse event; ARV = antiretroviral; bNAb = broadly neutralizing antibody; CD4 = clusters of differentiation 4; CD8 = clusters of differentiation 8; DNA = deoxyribonucleic acid; ECG = electrocardiogram; eGFR = estimated glomerular filtration rate; ESDD = early study drug discontinuation; ET = early termination; FSH = follicle-stimulating hormone; Gilead = Gilead Sciences; HBV = hepatitis B virus; HCV = hepatitis C virus; HIV = human immunodeficiency virus; HIV-1 = human immunodeficiency virus type 1; HIVDQoL = HIV-dependent quality of life; HIVTSQc = HIV Treatment Satisfaction Questionnaire change version; HIVTSQs = HIV Treatment Satisfaction Questionnaire status version; IV = intravenous; LEN = lenacapavir; PBMC = peripheral blood mononuclear cell; PK = pharmacokinetic(s); PSD = post study drug; RNA = ribonucleic acid; SC = subcutaneous; TSH = thyroid-stimulating hormone; Wk = week

a Screening Visit 2 will be performed once results of GS-5423 and GS-2872 sensitivity testing from Visit 1 are reviewed and participant is deemed eligible to proceed.

- b Refer to Section 6.3.11 for ESDD and post-ESDD 30-, 90-, 180-, 270-, and 365-day follow-up visits. Counsel participant regarding the importance of continuing a complete ARV therapy in accordance to standard of care, and refer participant to an appropriate HIV treatment facility.
- c Vital signs: blood pressure, pulse, and temperature. On dosing days for LEN + GS-5423 + GS-2872, vital signs should be recorded prior to start of study drug administration and 30 minutes (± 10 minutes) after completion of both GS-5423 and GS-2872 infusion, if coadministered or the GS-2872 infusion, if sequentially administered.
- d Refer to Table 6 for specific tests that are not on a standard chemistry panel (eg, amylase/lipase, uric acid).
- e CD4+ and CD8+ T-cell counts at post-ESDD 90-day follow-up visit only.
- f An FSH test is required for participants assigned female at birth who are younger than 54 years, have not undergone permanent sterilization, are not on hormonal contraception, and have stopped menstruating for at least 12 months but do not have documentation of ovarian hormonal failure; see Appendix 11.3.
- g Participants assigned female at birth of childbearing potential only. On dosing days, urine pregnancy test to be performed predose. A positive urine pregnancy test should be confirmed with a serum pregnancy test.
- h HIV-1 genotype and phenotype testing for participants with confirmed virologic failure and HIV-1 RNA ≥ 200 copies/mL. Refer to Section 6.3.9.2.
- i HIV reservoir sample (PBMC) and ECG to be collected at Day 1, Week 26, Week 52, Week 104, and every 12 months thereafter.

CCI

CCI

- n Serum PK samples for GS-5423 and GS-2872 will be collected in all participants as follows:
- Day 1: 0 hours (predose, ≤ 30 minutes prior to dosing of oral LEN) and within 5 minutes after the end of the second antibody infusion (GS-2872).
 - Week 26: 0 hours (predose, ≤ 30 minutes prior to dosing of SC LEN) and within 5 minutes after the end of the second antibody infusion (GS-2872).
 - Week 52 and subsequent dosing days: 0 hours (predose, ≤ 30 minutes prior to dosing of SC LEN) and within 5 minutes after the end of both antibody infusions (GS-5423 and GS-2872), if coadministered or the second antibody infusion (GS-2872), if sequentially administered.
 - A single any time sample at other scheduled visits.
- o Plasma samples for LEN will be collected in all participants as follows:
- Day 1: 0 hours (predose, ≤ 30 minutes prior to dosing of oral LEN) and within 5 minutes after the end of the second antibody infusion (GS-2872).
 - Week 26 and subsequent dosing days: 0 hours (predose, ≤ 30 minutes prior to dosing of SC LEN).
 - A single any time sample at other scheduled visits.

CCI

- q On visits when both HIVTSQs and HIVTSQc will be completed, HIVTSQs should be completed first.
- r Participants will take 2 oral LEN tablets on Day 1 at the clinic and self-administer 2 oral LEN tablets on Day 2 at home, CCI
- s Refer to Section 5.3. If coadministered, infusion of GS-5423 and GS-2872 will begin immediately following (up to 1 hour after) the last SC LEN injection. If sequentially administered, infusion of GS-2872 will begin at least 15 minutes following (up to 1 hour after) the completion of GS-5423 IV infusion. The exact date and time of study drug administration must be carefully recorded. Participants will remain in a monitored clinical setting for at least 30 minutes after completion of GS-5423 and GS-2872 infusion, if coadministered or GS-2872 infusion if sequentially administered. For the Day 1 and Week 26 visits and all subsequent dosing visits, all study drugs are to be administered

CCI

- u Participants may opt to continue study visits beyond Week 156 on the same schedule with study visits every 12 and 24 weeks between dosing visits (every 26 weeks) until the product becomes accessible to participants through an access program, is commercially available, or Gilead elects to discontinue the study, whichever occurs first.

Table 13-2. Study Procedures Table (Treatment Group 3)

Study Procedure	Screening		Randomized Phase						Extension Phase ^s				ESDD ^b	Post Study Drug Follow-up ^{cb}	
	Visit 1	Visit 2 ^a	Day 1	Wk 12	Wk 26	Wk 38	Wk 50	Wk 52	Wk 56	Wk 64, 90, 116, 142	Wk 76, 102, 128, 154	Wk 78, 104, 130, 156		PSD Day 30, 90, 180	PSD Day 270, 365
Visit Window (Days)			Within 28 Days of Screening Visit 2	± 6 Days					± 6 Days					± 6 Days	
Written informed consent	X														
Medical history	X	X													
Review concomitant medications	X	X	X	X	X	X	X	X	X	X	X	X	X	X	X
Review AEs	X	X	X	X	X	X	X	X	X	X	X	X	X	X	X
Complete physical examination		X	X										X		
Focused physical examination				X	X	X		X	X	X		X		X	
Height		X													
Weight		X	X	X	X	X		X	X	X		X	X	X	
Vital signs ^c		X	X	X	X	X		X	X	X		X	X	X	
Proviral DNA phenotype	X														
Proviral DNA genotype	X														
Chemistry ^d		X	X	X	X	X		X	X	X		X	X	X	
Hematology ^d		X	X	X	X	X		X	X	X		X	X	X	
TSH		X	X					X					X		
CD4+ and CD8+ T-cell count		X	X	X	X	X		X		X		X	X	X ^e	
Serum pregnancy test		X													

Study Procedure	Screening		Randomized Phase						Extension Phase ^s				ESDD ^b	Post Study Drug Follow-up ^{cb}	
	Visit 1	Visit 2 ^a	Day 1	Wk 12	Wk 26	Wk 38	Wk 50	Wk 52	Wk 56	Wk 64, 90, 116, 142	Wk 76, 102, 128, 154	Wk 78, 104, 130, 156		PSD Day 30, 90, 180	PSD Day 270, 365
Visit Window (Days)			Within 28 Days of Screening Visit 2	± 6 Days					± 6 Days					± 6 Days	
FSH ^f		X													
Urinalysis		X	X	X	X	X		X	X	X		X	X	X	
Urine pregnancy test ^g			X		X			X	X	X		X	X	X	X
HBV & HCV serology		X													
HIV-1 RNA		X	X	X	X	X	X	X	X	X	X	X	X	X	
HIV-1 genotype/phenotype ^h				X									X		
HIV reservoir assay (PBMC) ⁱ			X		X			X				X			
CCI															
eGFR		X	X	X	X	X		X	X	X		X	X	X	
ECG ⁱ		X	X		X			X				X			
Plasma storage samples for virology testing			X	X	X	X	X	X	X	X	X	X	X		
Immunogenicity (ADA) serum sample ^k								X		X		X	X	X	X
Serum PK samples (GS-5423 & GS-2872) ^{l, m}								X	X	X		X	X	X	X
Plasma PK sample for LEN ^{l, n}								X	X	X		X	X	X	X
Randomization			X												

Study Procedure	Screening		Randomized Phase						Extension Phase ^s				ESDD ^b	Post Study Drug Follow-up ^{cb}	
	Visit 1	Visit 2 ^a	Day 1	Wk 12	Wk 26	Wk 38	Wk 50	Wk 52	Wk 56	Wk 64, 90, 116, 142	Wk 76, 102, 128, 154	Wk 78, 104, 130, 156		PSD Day 30, 90, 180	PSD Day 270, 365
Visit Window (Days)			Within 28 Days of Screening Visit 2	± 6 Days					± 6 Days					± 6 Days	
HIV Treatment Preference Questionnaire			X		X			X				X			
HIVDQoL			X		X			X				X			
HIVTSQs ^o			X		X			X	X			X			
HIVTSQc ^o												X			
Continue baseline oral ART			X												
LEN oral administration ^p								X							
LEN SC administration								X				X			
GS-5423 IV infusion administration ^q								X				X			
GS-2872 IV infusion administration ^q								X				X			

CCI

ADA = antidrug antibody; AE = adverse event; ARV = antiretroviral; bNAb = broadly neutralizing antibody; CD4 = clusters of differentiation 4; CD8 = clusters of differentiation 8; DNA = deoxyribonucleic acid; ECG = electrocardiogram; eGFR = estimated glomerular filtration rate; ESDD = early study drug discontinuation; FSH = follicle-stimulating hormone; Gilead = Gilead Sciences; HBV = hepatitis B virus; HCV = hepatitis C virus; HIV = human immunodeficiency virus; HIV-1 = human immunodeficiency virus type 1; HIVDQoL = HIV-dependent quality of life; HIVTSQc = HIV Treatment Satisfaction Questionnaire change version; HIVTSQs = HIV Treatment Satisfaction Questionnaire status version; IV = intravenous; LEN = lenacapavir; PBMC = peripheral blood mononuclear cell; PK = pharmacokinetic(s); PSD = post study drug; RNA = ribonucleic acid; SC = subcutaneous; TSH = thyroid-stimulating hormone; Wk = week

a Screening Visit 2 will be performed once results of GS-5423 and GS-2872 sensitivity testing from Visit 1 are reviewed and participant is deemed eligible to proceed.

- b For participants who discontinue the study prior to Week 52, only a ESDD and 30-day follow-up visit is required. For participants who receive study drug in extension phase, refer to Section 6.3.11 for ESDD and post-ESDD 30-, 90-, 180-, 270-, and 365-day follow-up visits. Counsel participant regarding the importance of continuing a complete ARV therapy in accordance to standard of care, and refer participant to an appropriate HIV treatment facility.
- c Vital signs: blood pressure, pulse, and temperature. On dosing days for LEN + GS-5423 + GS-2872, vital signs should be recorded prior to start of study drug administration and 30 minutes (\pm 10 minutes) after completion of both GS-5423 and GS-2872 infusion, if coadministered or the GS-2872 infusion, if sequentially administered.
- d Refer to Table 6 for specific tests that are not on a standard chemistry panel (eg, amylase/lipase, uric acid).
- e CD4+ and CD8+ T-cell count at post-ESDD 90-day follow-up visit only.
- f An FSH test is required for participants assigned female at birth who are younger than 54 years, have not undergone permanent sterilization, are not on hormonal contraception, and have stopped menstruating for at least 12 months but do not have documentation of ovarian hormonal failure; see Appendix 11.3.
- g Participants assigned female at birth of childbearing potential only. On Week 52 and subsequent dosing days, urine pregnancy test to be performed predose. During the randomized and extension phase, a positive urine pregnancy test should be confirmed with a serum pregnancy test.
- h HIV-1 genotype and phenotype testing for participants with confirmed virologic failure and HIV-1 RNA \geq 200 copies/mL. Refer to Section 6.3.9.2.
- i HIV reservoir sample (PBMC) and ECG to be collected at Day 1, Week 26, Week 52, Week 78, Week 104, and every 12 months thereafter.

CCI

[figure not shown]
- l The exact date and time of collection of PK samples must be recorded. PK samples should be drawn from a separate catheter in the opposite arm from the one used for GS-5423 and GS-2872 IV infusions to avoid contamination. Refer to Section 6.3.6 for details.
- m Serum PK samples for GS-5423 and GS-2872 will be collected in all participants as follows:
 - Week 52: 0 hours (predose, \leq 30 minutes prior to dosing of oral LEN) and within 5 minutes after the end of both antibody infusions (GS-5423 and GS-2872), if coadministered or the second antibody infusion (GS-2872), if sequentially administered.
 - Week 78 and subsequent dosing visits: 0 hours (predose, \leq 30 minutes prior to dosing of SC LEN).
 - A single any time sample at other scheduled visits.
- n Plasma PK samples for LEN will be collected in all participants as follows:
 - Week 52: 0 hours (predose, \leq 30 minutes prior to dosing of oral LEN) and within 5 minutes after the end of the infusion of both antibodies (GS-5423 and GS-2872), if coadministered or the second antibody infusion (GS-2872), if sequentially administered.
 - Week 78 and subsequent dosing days: 0 hours (predose, \leq 30 minutes prior to dosing of SC LEN).
 - A single any time sample at other scheduled visits.
- o HIVTSQc will only be completed at Week 78. On visits when both HIVTSQs and HIVTSQc will be completed, HIVTSQs should be completed first.
- p Participants will take 2 oral LEN tablets at Week 52 at the clinic and self-administer 2 oral LEN tablets the following day (Week 52 + 1 day) at home.
- q Refer to Section 5.3. If coadministered, infusion of GS-5423 and GS-2872 will begin at least 15 minutes (up to 1 hour after) after SC LEN injection. If sequentially administered, infusion of GS-2872 will begin at least 15 minutes following (up to 1 hour after) the completion of GS-5423 IV infusion. The exact date and time of study drug administration must be carefully recorded. Participants will remain in a monitored clinical setting for at least 30 minutes after completion of GS-5423 and GS-2872 infusion, if coadministered or GS-2872 infusion, if sequentially administered. For the Week 52, 78, and 104 visits and all subsequent dosing visits, all study drugs are to be administered on the same day.

CCI

- s Participants may opt to continue study visits beyond Week 156 on the same schedule with study visits every 12 and 24 weeks between dosing visits (every 26 weeks) until the product becomes accessible to participants through an access program, is commercially available, or Gilead elects to discontinue the study, whichever occurs first.

